## **6.2. SREC Intervention**

The SREC device to be used in this study comes from a NIDA-funded SBIR contract for a standardized e-cigarette to NJOY LLC (a requirement for all grants funded under this Program Announcement). The SREC system consists of the SREC Device and the SREC Pods. The device is rechargeable via USB connection, and it measures 88 mm in length, 30mm in width, and 13 mm in depth/thickness. The device weighs 54 +/- 5g and the Filled Pod weighs 7.5g +/- 0.5g. The SREC Device contains a rechargeable 400 mAh lithium-ion battery cell to deliver power to the SREC Pods and the settings cannot be adjusted by the user. The SREC packaging pouch for each pod will be labeled "For Investigational Use Only." The SREC Pods will be tobacco, menthol, blueberry, or watermelon-flavored 1.9mL e-liquid in sealed disposable containers with 5% nicotine. SREC Pods have 0.3 mg/55mL of nicotine and deliver 55 mL puffs with about 300 puffs per pod. NJOY SREC has a Tobacco Product Master File on file with the Center for Tobacco Products (CTP) at the FDA with complete technical characteristics of the device, pod, and e-liquid as well as the SREC nicotine pharmacokinetic delivery and profile.

The 12-week SREC trial provides an adequate time for participants to adjust to the SREC (there is often a learning curve with using e-cigarettes) as well as to evaluate whether they can sustain a switch. We also based the duration of treatment on the frequent length of NRT trials (e.g., nicotine patch, gum, etc.). The SREC Pods are packaged two to a pack. At study visit 2, when the SREC is first given to the participant, study

staff will dispense four packs (8 pods) to each participant. Participants in the flavor choice condition can select the SREC flavor(s) based on their personal preference. Some participants may select only one flavor and others may want to try one of each during this week. All flavor selections are carefully tracked in the project database. During this week, participants will start experimenting with the smoking reduction strategies and with using the SREC with a goal to reduce their cigarette smoking by 75% by the end of that week. One pod a day should be sufficient for this initial week. Over time as participants get experience with the SREC and reducing their smoking, they can make decisions about how much, if any, use of SREC they prefer. We can adapt the number of pods dispensed at each visit based on their success with reduction and their level of SREC use. At each visit, study staff will review their use of cigarettes and SREC since the previous visit and make a decision with the participant about the amount of product they feel they need before their next study visit. For participants who smoke 20 cigarettes or less a day, the upper limit for SREC distribution will be one pod per day. For participants who smoke 21 or more cigarettes a day the upper limit for SREC distribution will be two pods a day. Additionally, at each visit, participants in the flavor choice condition will continue to select the flavor from the four options based on personal preference and success with reduction. Study staff may encourage participants to try other flavors if they are struggling to reduce their cigarettes, but otherwise will not direct or suggest flavors to the participants.

Use of SREC and compliance with substituting SREC for cigarettes will be assessed via self-report and by return of all SREC pods that have been distributed at each study visit. All the open, returned pods will be weighed. Study staff will track the number and flavor of SREC pods dispensed to the participant at each visit. Participants will be instructed to return for their next study visit with all of these pods, regardless of whether they are empty or not. Participants will earn \$20 at each of these visits if they return ALL the pods they were given at the previous visit. Compliance with SREC is also assessed via self-report of use on the daily use surveys (week 2 through week 14) as well as at each of the study visits at weeks 3, 4, 6, 8, 11, and 14.

We will monitor both SREC (and any other e-cigarette use) and cigarette use throughout the study in order to ensure that participants are not creating a pattern of increased product use over an extended period of time. However, in the early stages of using SREC, an increase in nicotine exposure may occur as participants experiment with using the new device and practice the strategies from the behavioral intervention. As they learn which cigarette reduction strategies work and which do not, and assess their responses to the SREC (e.g., do they like the taste, is it pleasurable, does it reduce any urges or cravings for a cigarette), a temporary increase in use and exposure to nicotine is neither unexpected nor worrisome. Participants will be informed during the consent process and again during health coaching that over time if they use the SREC without reducing the amount of cigarettes they smoke they may increase their overall nicotine exposure which may increase withdrawal symptoms if they decide to quit. We will limit the amount of SREC dispensed as noted previously to limit the extent to which participants can increase their nicotine exposure. Nicotine exposure is difficult to assess from simple measures of product use. The amount of nicotine a person is exposed to is influenced by a number of factors beyond the amount of cigarettes and e-cigarettes used per day. Race, gender, nicotine metabolism, the level of nicotine dependence, the way in which a smoker smokes the cigarette (puff duration, volume, velocity and inter-puff intervals), the amount of nicotine present in the cigarette, and the presence of menthol in the cigarette all influence a given smoker's nicotine exposure. Health coaches will track the amount of product use (both cigarettes, SREC, and any other e-cigarettes) throughout the study and will provide feedback to participants if they are only increasing their use of SREC without decreasing cigarettes. Starting with the week 2 visit, the coaching discussions are focused on developing strategies for decreasing their cigarette use and problem-solving how to manage any difficulties associated with this process. Health coaches will also provide feedback based on the Adverse Event reports provided at each study visit, particularly those that are associated with over exposure to nicotine. We have an upper limit on the number of pods that will be dispensed at each visit to limit the amount of study provided nicotine. Finally, the study PI, study medical monitor, or the DSMB can decide to stop dispensing SREC pods to participants if their use or adverse events warrants; the DSMB will review reports quarterly during the intervention period but will also hold phone and web meetings as needed to review problematic adverse event cases.

We will store the SREC device and all pods in a locked cabinet in a locked room which only study staff who interact with participants can access. The SREC pods are packaged two to a pack and each pack is marked with tracking numbers that will be entered into a spreadsheet when distributed to participants.

Possible side effects of using e-cigarettes, whether the SREC or any other ENDS, include throat irritation, dry cough, mouth irritation, nausea, headaches, and dizziness. Less frequently reported side effects include: sore throat, dry mouth, shortness of breath, and mouth ulcers. Overuse of any product containing nicotine (or using multiple nicotine containing products) may increase the risk of nicotine toxicity. Although the use of SREC along with cigarettes in a research study warrants caution and careful monitoring, it is important to note that studies conducted to date with dual users of cigarettes and ENDS products demonstrate that using both products appear to be safe with few problems of nicotine toxicity. Symptoms of nicotine toxicity include pallor (pale appearance), cold sweat, nausea, excessive salivation, vomiting, diarrhea, tremor, mental confusion, and overall weakness. The likelihood that participants would continue using SREC and smoking cigarettes at levels that would cause problems is small; however, we will assess symptoms of nicotine toxicity at every study visit and will take all necessary steps to minimize any risks associated with using the SREC while continuing to smoke. Study staff will provide an information sheet and instruct participants how to identify symptoms of nicotine toxicity, and to reduce their cigarette smoking and use of SREC to avoid them. If needed, study staff will limit the distribution of SREC pods and consult the study safety monitor, [name], to determine next steps (see below).

Finally, another possible side effect of regular e-cigarette use is developing an EVALI; however, the likelihood of developing an EVALI while using the SREC is minimal. According to the CDC's recent investigation, EVALI cases were associated with vaping THC and using products purchased from non-licensed vendors (e.g., off the street, from friends or family). In order to minimize the risk of developing an EVALI, enrolled participants must agree to use only the study provided SREC products and to not modify the device or e-liquid in any way. Study staff will provide participants with information and guidance on EVALI from the CDC and instruct participants how to identify the early signs and symptoms of an EVALI. Symptoms reported from the recent EVALI outbreak include: respiratory symptoms, including cough, shortness of breath, or chest pain; gastrointestinal symptoms, including nausea, vomiting, stomach pain, or diarrhea; and nonspecific constitutional symptoms, like fever, chills, or weight loss. Additionally, study staff will assess presence and severity of symptoms associated with EVALI along with any e-cigarette products used (SREC or non-SREC) at each study visit and include this information with any potential AE or SAE reporting.

At each study visit following week 2, adverse events (AE) and unexpected problems (UPs) with the SREC are collected using a standardized AE Patient Query Form adapted from [name] prior research studies using NRT while reducing cigarettes. This form is stored in a REDCap database. AEs discovered outside of study visits, such as through a phone call or other administrative contact (e.g., appointment reminder or rescheduling calls), will also be documented using the standardized AE form and followed up with to assure participant safety. Clinical staff interviewers are the first line of staff to monitor and assess AEs and UPs. Staff are instructed to notify [name] of these events so that a plan to can be put into place and appropriately monitored. However, [name] will also receive an automatic notification from REDCap upon submission of every AE report in order to trigger a review. The study safety monitor ([name]) will review, adjudicate, and document decisions or request that additional details be gathered from the participant, all within the secure UIC REDCap web portal. Using this system, real-time AE reports can be generated at any time for the DSMB, UIC IRB, and/or NIDA, for both regularly scheduled reviews as well as in the event of any SAEs requiring expedited reviews. SAEs will be immediately reported to the medical monitor, [name] and to the IRB. [name] will address these with the participant to ensure that the participant is linked with appropriate follow-up medical care.

### **6.3. Surveys**

We will collect data via several different processes: 1) Online/In-person assessments (questionnaires and physiological markers; vital signs); 2) Automated email prompts providing web or text-based links for participants to report cigarette and SREC use at the end of each day; 3) EMA app during two separate 7-day periods (weeks 1 and 3); and 4) web or phone-based questionnaire for the one-month follow-up. All participants in both conditions receive all assessments.

Table 2 presents the timeline of the constructs assessed. Proposed measures for the questionnaires are based on established scales/measures and were selected to harmonize with ongoing national surveys (e.g., PATH- Population Assessment of Population and Health Study). All measures will be ones with good

psychometric properties and that we have used in prior research and may be modified based on need to harmonize with other SREC studies.

Table 2: Assessments	Week Number															
	1	2	3	4	5	6	7	8	9	10	11	12	13	14	18	
Demographics	x															
Medical History/Perceived Health	x															
Respiratory Symptom Q's (SGRQ) 	x													x	x	
Body Weight and Height	x													x		
Vital Signs: e.g., BP, heart rate	x	x	x	X		x		x			x			x		
Smoking and total tobacco use history (all forms combustible and non); patterns and quit attempts; prior cessation medication use	x															
Nicotine dependence: FTND  , WISDM 	x													x		
Breath CO	x	x	x	X		x		x			x			x		
Pregnancy test (female only)	x					x					x					
Withdrawal symptoms (Minnesota Nicotine Withdrawal Scale; Wisconsin Withdrawal Scale  )	x	x	x	X		x		x			x			x	x	
Craving and urges (QSU-brief) 	x	x	x	X		x		x			x			x		
Satisfaction/Pleasure with cigarettes/e-cigs; Subjective experience; appeal 	x	x	x	X		x		x			x			x		
Motivation to reduce and to quit smoking (rating scale)	x													x	x	
Motivations to use E-cigs	x													x		
E-cig Expectancies	x													x		
Intentions to use E-cigs	x	x	x	X	x	x	x	x	x	x	x	x	x	x	x	
Confidence to reduce cigarettes and quit (rating scale)	x													x		
Tobacco use in social network/household	x													x		
Social support for reduction/quitting	x													x		
Mood: PANAS 	x													x		
Alcohol, Marijuana and Substance Use	x													x		
Adherence/Use of SREC			x	X	x	x	x	x	x	x	x	x	x	x		
Daily Use of Cigarettes/SREC	x	x	x	X	x	x	x	x	x	x	x	x	x	x	x	
Adverse Events (e.g., throat irritation, nausea)			x	X	x	x	x	x	x	x	x	x	x	x		

A. A **Comprehensive questionnaire** (baseline and 14-Week End of Treatment visits) will be completed in-person to assess key constructs [e.g., sociodemographics, tobacco and nicotine use (history, dependence, attitudes, motivations, intentions, perceived harm), tobacco environment, cessation history and intentions, and other substance use]. Each questionnaire will take approximately 30 - 40 minutes to complete. Shorter **brief surveys** (5-7 minutes to complete) will be completed at weeks 2, 3, 4, 6, 8, and 11. These measures serve as important descriptors of our sample, serve as covariates or moderators in our analyses, and serve as predictors of success in reducing cigarettes and switching to SREC over time.

B. A **daily use survey** completed online via REDCap from an emailed or texted survey link starting at the week 2 visit through the week 14 visit (over the 12 treatment weeks) to assess the use of cigarettes, SREC, and any other e-cigarette/nicotine vaporizer. Each of these surveys will take about 1 minute to complete. This brief survey will serve as an indicator of change in patterns of use as well as a way for the Clinical Interviewer Staff to track progress with cigarette reduction and to monitor nicotine exposure during the treatment phase. Daily surveys ask about the number of cigarettes smoked and the number of SREC or other e-cigarette episodes on the previous day (an episode is defined as 15 puffs or a period lasting about 10 mins). We also ask if the participant finished a pod on the previous day.

C. **Two, week-long waves of EMA data collection** using a **study provided smartphone**, the first wave will take place immediately following completion of the baseline questionnaire (week 1 visit through week 2 visit), and the second wave will take place starting at the week 3 visit through the week 4 visit. The first week of EMA provides the baseline comparison with combustible cigarettes to the second EMA wave when participants will have one week of experience with using the SREC and some practice cutting down on their cigarette smoking. Each EMA wave will cover 7 consecutive days, ensuring both weekday and weekend sampling.

We will provide a study smartphone with the custom app installed to each participant. The app is specifically developed for the EMA data collection, which will conduct brief tobacco use interviews through random prompts and participant-initiated recordings of cigarette/SREC/e-cigarette use episodes. The EMA app will “beep” randomly between 5 -7 times a day during waking hours, and ask questions about the participant's daily experiences, such as what they are doing, who they are with, and how they are feeling. It will also ask about cigarette/SREC/e-cigarette use and use of alcohol and marijuana. These interviews will take about two minutes each to complete. Participants also initiate an interview on the app each time they smoke a cigarette or use the SREC device (or other e-cigarette/vaporizer). Each of these interviews also take about 3 minutes to complete. When participants event-record cigarette/SREC use, they respond to questions about their immediate context and mood, but also answer questions related to their cigarette/SREC use. First, they will indicate which product they are using, and subsequent questions are tailored to that product. They will be asked about quantity (e.g., how many cigarettes, how many puffs), how much they wanted to use that specific product, how strong their urge was to smoke (asked regardless of product used), how much they “craved” a cigarette (asked regardless of product used), and potential withdrawal and nicotine-related symptoms (restless, impatient, hungry, sick, buzzed). They will also be asked about “throat hit” and any throat irritation. Other withdrawal symptoms are already included in our mood assessments (e.g., irritable, trouble concentrating, anxious). We will train participants individually on how to use the app. Given the ubiquity of smartphones, participants rarely have difficulty completing prompts. After the first day, the trainer will call participants to assess compliance and assist with problems. Research staff will be available via phone and email throughout the week to respond to research or technology issues with the phone or app.

D. **Semi-structured, debriefing interview** (see Appendix: ED Debriefing Interview) following each wave of EMA data collection this interview will be conducted to assess compliance with the EMA protocol, reactivity to carrying the ED, a review of data quality, and obtain feedback on the EMA data collection experience. The debriefing interview will take about 20 minutes.

E. **Carbon-monoxide (CO) level** in expired air will be measured using a digital monitor at each study visit allowing us to examine changes in CO over time along with changes in patterns of cigarette and SREC use. There are no required qualifications or credentials for the use of a carbon monoxide (CO) monitor. It is a very basic device that simply requires a subject to exhale into a disposable (single use), mouthpiece attached to the digital monitor. All staff involved in the implementation will be trained in the protocol, which includes the following:

1. A member of the research staff will insert a new mouthpiece, turn the monitor on and hand the monitor to the participant.
2. The participant will be instructed to inhale, hold the breath for 15 seconds, and then exhale the entire breath through the mouthpiece into the digital monitor while following the on-screen prompts.

F. **Urine pregnancy tests** will be administered to female participants of childbearing age (defined as 55 years old and younger) during the Week1/Enrollment visit and every 5 to 6 weeks during the study; those with positive test results (a result indicating pregnancy) will be removed from the study.

G. Other **vital signs** will be measured at study visits including height and weight (baseline and end of treatment), blood pressure and pulse (at every study visit).

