**Table 1: Timeline of Assessments and Procedures**

Week	Procedures	Modality	Visit Duration (in minutes)
0	Screening eligibility	On-line and phone	
1	CO; pregnancy test; baseline questionnaires on tablet (if not already completed); vital signs; height and weight; EMA training; go home with EMA and smoke usual cigarettes	In-person visit	90-120
2	De-brief EMA; CO; Counseling about reduction and switch; brief questionnaire; given week supply of SREC; daily reports of use	In-person visit; daily text/web reports of use	60
3	Return used pods; CO; Brief counseling to problem solve reduction and switch; given new week supply of SREC; start EMA	In-person visit; daily text/web reports	40
4	Debrief EMA week; return used pods; CO; brief review of progress and problem-solve; given 2-week supply of SREC	In-person visit; daily text/web reports of use	40
5	Daily reports of use via text/web	Daily Text/web reports of use	
6	Brief check-in to give next 2-week supply of SREC; return used pods; CO; continue daily reports of use via text/web; pregnancy test	In-person visit; daily text/web reports of use	20
7	Daily reports of use via text/web	Daily Text/web reports of use	
8	Brief check-in to return used pods; given next 2-week SREC supply; CO; continue daily reports of use via text/web	In-person visit; daily text/web reports of use	20
9	Daily reports of use via text/web	Daily Text/web reports of use	
10	Daily reports of use via text/web	Daily text/web reports of use	
11	Brief check-in to return used pods; CO; given next supply of SREC; continue daily reports of use via text/web; pregnancy test	In-person visit; daily Text/web reports of use	20
12	Daily reports of use via text/web	Daily text/web reports of use	
13	Daily reports of use via text/web	Daily Text/web reports of use	
14	End-of-treatment full assessment battery; CO; vitals; height and weight; collect SREC device and remaining pods; daily reports of use surveys end	In-person	60
18	Brief follow-up about cigarette and ENDS use over past month	Web/phone based	15

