**Baseline/Enrollment Visit Week 1.** The first visit begins with the final set of screening assessments: CO > 3ppm and negative pregnancy test for female participants. Once the screening is complete, participants who remain eligible will start the consent process. Staff describe the study, answer all questions, ensure understanding of the study information, and re-assess interest in participating. Participants who remain interested will be asked to sign the informed consent form. Participants will complete the baseline questionnaire on a tablet, and participants will have vital signs taken (blood pressure, heart rate, height, weight). Participants will also be trained on the EMA protocol (see below for more details) and given instructions to go home and smoke as they usually do. **The purpose of this first EMA week is to provide baseline data about the participant's smoking pattern which will be compared to their SREC/cigarette use pattern after switching.**

**Week 2 Visit.** Participants will complete a brief questionnaire and complete an expired CO assessment. Study staff conduct a debriefing interview to review the EMA week and their compliance with the protocol. Participants will be randomly assigned to the two flavor conditions, stratifying for gender. Those participants assigned to the choice condition will select from four SREC flavors (tobacco, menthol, watermelon, and blueberry) based on their preference. Participants assigned to the usual flavor condition will receive tobacco pods if they smoke regular cigarettes and menthol pods if they smoke menthol cigarettes. Participants in both conditions will receive **brief behavioral counseling** (see below for more details) on reducing their combustible cigarette use and using SREC as a substitution for cigarettes. Starting this week, participants begin to receive daily email or text prompts (based on participant's preferred mode of communication) to complete a brief online survey on their use of cigarettes, SREC, and non-SREC e-cigarette use each day.

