## 9.0 Data Analysis

**Aim 1. Examine whether conventional cigarette smokers can significantly reduce their combustible cigarette use by switching to SREC.** We will have assessments of the amount of SREC and combustible cigarettes used every week for 12 weeks. SREC/e-cigarette use per day is captured by the total number of e-cigarette episodes defined as about 15 puffs or a period lasting about 10 minutes. Both of these outcomes will be modeled as count data (average # cigs/day and SREC episodes/day for each week) using a mixed-effects Poisson regression model (or Negative Binomial model if the Poisson assumption of equality of mean and variance is not met). In these analyses, we will examine primarily linear and curvilinear changes across time using orthogonal polynomial transforms, in order to assess the independent effects of these two types of trends, which will be treated as random effects to allow heterogeneity across subjects in the time trends. These time trend analyses will allow us to investigate the **sustainability of reductions in cigarette use and changes in SREC use**. In addition to the effect(s) of time, the main independent variable is group (usual flavor or flavor choice). Although we expect the group effect to be consistent across the 12 weeks, we will test whether the group effect varies across time (i.e., group by time interaction). For example, it may be likely that differences between the groups increase over time if the usual flavor group more rapidly relapses back to smoking cigarettes and gives up on their SREC. Our primary endpoint will be the model-based estimate of the group difference at the final 12-week timepoint (study week 14). We will also consider the proportion of participants who achieve total abstinence from combustible cigarettes at the end of the 12-week trial (defined as no cigarette smoking in the past 7 days and confirmed by CO < 3 ppm; see power section). Although our primary endpoint is the end of the 12 weeks of treatment, (week 14) we will also evaluate effects at the one-month follow-up. In terms of these primary outcomes, we will further examine the degree to which

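### The daily cigarette survey starts when SREC is dispensed and ends when it is collected, so Aim 1 has no same-scale measure of usual smoking and week 18 has no comparable abstinence measure

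*Combined protocol and SAP*

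**What the plan says.** - Section 6.3 (Surveys), item B, runs the daily use survey "starting at the week 2 visit through the week 14 visit (over the 12 treatment weeks". It asks for the previous day's count.
- In section 6.0, the week 2 row of Table 1 puts the first SREC supply and the first daily reports at the same visit: "given week supply of SREC; daily reports of use". The Week 2 Visit text agrees: "Starting this week, participants begin to receive daily email or text prompts". The week 14 row collects the device and pods and ends the daily reports.
- Section 6.1 sets a goal of at least a 75% cut by the end of the first SREC week.
- The week 1 EMA wave is meant to "provide baseline data about the participant's smoking pattern which will be compared to their SREC/cigarette use pattern after switching" (section 6.0, Baseline/Enrollment Visit).
- At week 18, Table 1 lists "Brief follow-up about cigarette and ENDS use over past month", by web or phone. Neither Table 1 nor Table 2 schedules CO then.
- Table 2 nevertheless marks the row "Daily Use of Cigarettes/SREC" at weeks 1 and 18 as well as during treatment.
- Section 9.0, Aim 1, models weekly averages over 12 weeks. The primary endpoint is the group difference at week 14. Abstinence at the end of treatment is "defined as no cigarette smoking in the past 7 days and confirmed by CO < 3 ppm", and "we will also evaluate effects at the one-month follow-up". No baseline cigarettes-per-day variable is named.

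**The concern.** The title question of Aim 1 is whether smokers can cut down by switching. Answering it for a person needs usual smoking and later smoking on one scale. The instrument behind the modelled outcome has no reading before SREC is in hand, and the first week it does cover is the week in which most of the fall is meant to happen.

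Three things depend on a pre-switch reference: the within-person answer to the Aim 1 question; the description of flavor choice by level of reduction (section 9.0); and Aim 2, which takes each person's usage change from the 12-week count model and relates it to health measures whose baseline is week 1. A baseline count could also serve as a covariate in the Aim 1 model.

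At the other end, week 18 is the only look at smoking after SREC is collected, and it uses a different recall period and no CO.

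**Working it through.** **1. Survey window.** Week 2 to week 14 is 14 − 2 = 12 weeks, which reproduces the plan's figure. The run-in is 2 − 1 = 1 week and the period after SREC collection is 18 − 14 = 4 weeks. Coverage is 12 of 12, 0 of 1 and 0 of 4. Section 9.0 does not name the survey as its source, but the 12 weeks and the definition of an e-cigarette episode match section 6.3, item B. Because the survey asks about the previous day, a survey on the day of the week 2 visit could catch at most one pre-SREC day.

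**2. What fills the gaps.**

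| Period | Source of cigarette counts in the text | Recall | CO |
|---|---|---|---|
| Week 1 to 2 | EMA app; baseline questionnaire (items not given) | At event or prompt for EMA | Weeks 1, 2 |
| Week 2 to 14 | Daily survey; EMA again from week 3 to 4 | Previous day for the survey | Every visit |
| Week 18 | One web or phone survey | Past month | None |

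**3. Does the 12-week slope stand in for reduction?** Take the upper usual rate in section 12.0, 15 per day, and suppose the 75% goal is met: 15 × 0.25 = 3.75, a fall of 11.25.
- If the fall is immediate and held, all 12 weekly means are 3.75 and the slope is zero. A person who never changes has 12 means of 15 and also a zero slope. True reductions are 75% and 0%.
- If the fall is even over the 7 days, the count on day d is 15 − 11.25 × d/7. The first weekly mean is 15 − 11.25 × 4/7 = 8.57. Of the 11.25, 15 − 8.57 = 6.43 (57%) is already inside that mean, and 4.82 (43%) is left for the trend.

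The paths are assumptions. They show that the slope misses some or all of an early fall. In Aim 2 that slope is set against health changes measured from before the switch.

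**4. What if reduction is computed across instruments?** Let q be the week 1 EMA count divided by what the daily survey would have recorded that week. The documents give no value for q, so a range is shown. Apparent change = (1 − true cut)/q − 1.

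| q | No true change | True 25% cut | True 75% cut |
|---|---|---|---|
| 0.8 | +25% | −6% | −69% |
| 0.9 | +11% | −17% | −72% |
| 1.0 | 0% | −25% | −75% |
| 1.1 | −9% | −32% | −77% |
| 1.2 | −17% | −37.5% | −79% |

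**5. Does this reach the group comparison?** Write Y for the week 14 count and B for the baseline the survey would have given, with c for flavor choice and u for usual flavor. The ratio of relative change is [Y_c/(qB_c)] / [Y_u/(qB_u)] = (Y_c/B_c)/(Y_u/B_u). A q common to both arms cancels. The primary endpoint uses Y_c and Y_u only, so q does not enter it.

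**6. Week 18 abstinence.** The definition needs 7 days without cigarettes and a CO reading. The CO part is not scheduled, and the survey is described as covering the past month. The definition therefore cannot be applied, and no other is given.

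**The case against.** Much of the opposing case stands.

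- A reader might infer that the primary result is biased. It is not: it is a randomised contrast at week 14 within one instrument. The Aim 1 hypothesis is also between groups, and baseline precedes randomisation, so a common instrument ratio cancels.
- A reader might infer that the sustainability analysis is compromised. Section 9.0 ties sustainability to time trends over the 12 treatment weeks, all on one survey. Persistence after SREC is collected is a separate question, touched only by the week 18 evaluation.
- The statement of purpose for the first EMA week might suggest that EMA counts will be divided into survey counts. Section 6.3, item C, and section 9.0, Aim 4, instead compare EMA week 1 with the second EMA wave on the same app. No cross-instrument percentage is planned. It is simply the only route the text leaves open for cigarettes per day from usual smoking to week 14.
- A reader might assume that EMA undercounts baseline smoking. The documents do not show this. Random prompts also ask about cigarettes, event records ask for quantity, and there is training, a call after the first day and a debrief that corrects entries.
- Table 2 lists constructs, and the comprehensive questionnaire, given at baseline and week 14, covers tobacco use. A matching cigarettes-per-day item cannot be excluded, but none is described. CO is a same-instrument series from week 1 to week 14, but it is not a cigarette count.
- At week 18 both arms get the same survey, so a group contrast there is like for like. Only the change from week 14 to week 18 crosses definitions.
- A daily survey in week 1 adds self-monitoring when people should smoke as usual. That is a real but small cost, since EMA already asks them to record each cigarette that week.

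**Conclusion.** The point holds as a gap in measurement, of secondary importance. As written, the plan has no pre-switch cigarettes-per-day value on the instrument behind the Aim 1 outcome. Within-person reduction, the level-of-reduction description and the Aim 2 usage-change estimates must therefore either cross instruments or rely on a slope that misses part or all of an early fall. CO-confirmed abstinence cannot be computed at week 18.

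The size is unknown. The table for q shows what a difference of up to 20% either way would do and is not an estimate. Not affected are the week 14 randomised contrast, the 12-week trends, and the between-group hypothesis as long as the instrument ratio is equal in both arms. The conclusion assumes that the text of sections 6.0 and 6.3 governs over the extra marks in Table 2; if a daily survey is in fact sent around weeks 1 and 18, most of the gap closes once the text says so.

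**What to change.** 1. Send the existing REDCap daily survey during week 1 and for the 7 days before week 18, and reconcile the Table 2 marks at those weeks with Table 1, the Week 2 Visit text and section 6.3, item B.
2. In section 9.0, define reduction as survey week k against survey week 1, use the same reference for the Aim 2 usage change, and enter survey week 1 as a baseline covariate in the Aim 1 model.
3. Report self-reported 7-day abstinence at weeks 14 and 18, beside the CO-confirmed week 14 result, so that the change between the two weeks is like for like.

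Cost: 7 + 7 = 14 automated one-minute surveys, about 14 minutes per participant, and a short amendment, with no added visits or staff. The downside is slight extra self-monitoring in the baseline EMA week. If the surveys are not added, the minimum is to name the source of cigarettes per day at weeks 1 and 18, use one common questionnaire item at weeks 1, 14 and 18, and label any cross-instrument change as secondary.
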